### **Procedure**

All data will be collected on qualtrics. Interested individuals will sign up using the online subject pool, SONA. Part 1 will be completed online, either in the lab or at their own personal computer. After electronically confirming consent (using the provided informed consent sheet from TAMU Research Compliance and Biosafety), participants will complete demographics, followed by the Alcohol Use Disorder Identification Test, a measure of perceived behavioral control, a measure of delay-discounting, the Daily Drinking Questionnaire-Revised, the Young Adult Alcohol Consequences Questionnaire, Protective Behavioral Strategies (PBS), the Personal Assessment of Responsible Drinker Identity Scale, Alcohol Use Contemplation/Intention measure. After these measures have been completed, participants will then be randomly assigned to one of four conditions. In one condition, participants will be asked to only write about a negative drinking event. In the second condition, participants will be asked to write about a negative drinking event in addition to recalling facts about the same event. In the third condition, participants will be asked to write about a negative drinking event and will then complete a counterfactual task. The task will ask the individuals to list three counterfactual strategies about the negative event, future situations these strategies could be used, as well as obstacles to using the strategies. The task will wrap up by asking these participants to indicate intention to use those strategies in the future. In the fourth condition, participants will be asked to complete the Personalized Normative Feedback (PNF). Participants in all conditions will complete perceptions of protective behavioral strategy norms questions, the Alcohol Use Contemplation/Intentions measure, a measure of perceived behavioral control as well as intentions to use protective behavioral strategies.

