## 9.0

### Study Population

#### 9.1 Number of Participants

Approximately how many subjects do you plan to enroll?

1500

Provide the rationale for the number of subjects requested (for example, power analysis, sponsor requirements, etc.).

To have adequate statistical power to compare across the three conditions, assuming that not all participants will qualify after the baseline study and there will be some participant attrition across the follow up sessions.

Will human subjects be used from the Qatar population?

Yes  No

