Official Title of Study: Alcohol PBS and Thinking about the Past

NCT Number: Not Assigned

Unique Protocol ID: IRB20201070D

Date of Document: 09/10/2021

Planned Analysis

[figure not shown]
Statistical Design: The statistical design uses a multilevel structural equation model. The model will compare three conditions: Negative Event, Negative Event w/ a detailed description of the event, Negative Event w/ generated Counterfactuals to reduce future negative events, and Protective Behavioral Strategy Personalized Normative Feedback (PBS-PNF). Each condition will be used to predict protective behavioral strategies. Protective behavioral strategies will then predict alcohol and alcohol consequences. As the conditions are at the between-subject level, the hypotheses are specific to between subject effects, however, the data will be modeled at both the within- and between- subjects level (see Figure 1). In order to decompose variance across levels, all level 1 variables will be centered at the person level while all level 2 variables will be centered at the grandmean. Only weeks during which participants consume alcohol will be included in the analysis, as the intervention target (PBS) only occurs on drinking days.

Covariates: At level 1, we will control for week of study and number of drinking days. At level 2 we will control for biological sex at birth.

Hypothesis 1: Relative to control, the counterfactual condition will result in significantly more use of PBS during drinking days and will be *at least* non-inferior to PBS personalized normative feedback (significant effect of path a).

Hypothesis 2: Relative to control, the counterfactual condition will exert a significant specific indirect effect on alcohol problems through PBS (H2 = path a x path b).

Hypothesis 3: Relative to control, the counterfactual condition will exert a significant total indirect effect on alcohol problems through PBS use and alcohol use ($H3 = H2 + [\text{path a} \times \text{path c} \times \text{path d}]$).

Mplus Code:

usevar are CFcondition PBSPNFcondition NegEventcondition L1PBS L1Drinks
L2PBS L2Drinks Problems;

within are L1PBS L1Drinks;

between are CFcondition PBSPNFcondition NegEventcondition L2PBS L2Drinks;

cluster = ID;

analysis:

estimator = mlr;

PROCESSORS = 2;

type = twolevel;

model:

%within%

L1Drinks on L1PBS;

Problems on L1Drinks L1PBS;

[L1Drinks @0];

[L1PBS @0];

%between%

L2PBS on CFcondition(a);

L2PBS on PBSPNFcondition;

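### H2 and H3 have no named test; the delta-method z that the code implies is conservative for H2, and for H3 as the text defines it, when the paths are imprecise, and a Monte Carlo interval would recover that power

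*SAP*

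**What the plan says.** The SAP's H2 is that "the counterfactual condition will exert a significant specific indirect effect on alcohol problems through PBS", defined as "H2 = path a x path b". H3 is a total indirect effect, defined in the text as H2 plus path a × path c × path d. Each is to be significant. The SAP states no alpha, sidedness, test or interval for either. Its only interval is the 95% confidence interval in the exploratory equivalence comparison with personalized normative feedback.

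The Mplus code has "estimator = mlr" and "type = twolevel" and computes H1, H2 and H3 as new parameters in Model Constraint. It requests no interval, no bootstrap and no parameter covariances. H2 is coded as a × b, in line with the text. H3 is coded as `H2+(c*d)`, without path a in the second term.

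On precision, Protocol section 9.1 plans 1500 participants, with this rationale: "To have adequate statistical power to compare across the three conditions". The Procedure section says "participants will then be randomly assigned to one of four conditions". Section 9.1 expects that "there will be some participant attrition across the follow up sessions" but gives no rate. The SAP adds that "Only weeks during which participants consume alcohol will be included in the analysis". The number analysed is therefore below 1500 by an unknown amount.

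**The concern.** New parameters in Model Constraint under MLR are reported with a delta-method standard error and a symmetric z. For a product of two estimates this is a poor approximation unless at least one factor is estimated precisely, because the product is skewed and sharply peaked near zero. If z_a and z_b are the two estimates divided by their standard errors, the delta-method statistic is z_a × z_b / √(z_a² + z_b²), which is always smaller than the smaller of the two.

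For example, suppose both paths come out at z = 2.5, each with two-sided p of about 0.012. The delta-method z for the product is 2.5/√2 = 1.77, p of about 0.077, and H2 fails although both of its links are individually clear.

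What is at stake is power for two of the three hypotheses, in a trial whose analysed sample may fall well short of enrolment.

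**Working it through.** **No figure to reproduce.** The documents give no power, effect size or alpha for H2 or H3, so everything below rests on stated assumptions.

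**Inputs**
- From the documents: 1500 enrolled, four conditions.
- Assumed: equal arms; analysed N of 1500, 900 or 450 across all four arms; standardised effect on path a of 0.1 to 0.4; standardised |b| of 0.05 to 0.30; two-sided 5%; normal estimates; path a independent of the other paths.

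**Formulas**
- z_a = d_a / √(2/n), with n = N/4, because the counterfactual dummy is compared with the omitted arm.
- z_b = |b| / √((1 − b²)/N), because path b uses all participants.
- Delta test: significant when |z_a z_b| / √(z_a² + z_b²) exceeds 1.96.
- Monte Carlo 95% interval in its large-draw limit: excludes zero when P(ab < 0) = Φ(z_a)Φ(−z_b) + Φ(−z_a)Φ(z_b) is below 0.025 or above 0.975.

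Example for N = 1500, d_a = 0.2, |b| = 0.10: z_a = 0.20/√(2/375) = 2.74 and z_b = 0.10/√(0.99/1500) = 3.89. At these values the delta z is 2.74 × 3.89 / √(2.74² + 3.89²) = 2.24, against 2.74 for path a alone.

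**H2 power** (1,000,000 or more simulated pairs of estimates per setting)

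| N | d_a | \|b\| | z_a | z_b | Delta | Monte Carlo |
|---|---|---|---|---|---|---|
| 1500 | 0.2 | 0.05 | 2.74 | 1.94 | 18.1% | 35.4% |
| 1500 | 0.2 | 0.10 | 2.74 | 3.89 | 61.6% | 75.3% |
| 1500 | 0.2 | 0.20 | 2.74 | 7.91 | 76.2% | 78.2% |
| 1500 | 0.2 | 0.30 | 2.74 | 12.18 | 77.4% | 78.2% |
| 1500 | 0.4 | 0.10 | 5.48 | 3.89 | 96.0% | 97.3% |
| 900 | 0.3 | 0.10 | 3.18 | 3.02 | 56.3% | 74.3% |
| 900 | 0.3 | 0.20 | 3.18 | 6.12 | 86.3% | 88.8% |
| 450 | 0.4 | 0.10 | 3.00 | 2.13 | 26.8% | 45.7% |
| 450 | 0.3 | 0.30 | 2.25 | 6.67 | 57.5% | 61.4% |

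Over the whole grid the gain runs from 0 to 19 points. It is largest when both z values are around 2 to 4. Once z_b is about 8 or more it is 2 points or less: path a alone then caps power, at 78.2% for N = 1500 and d_a = 0.2.

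**H2 type I error with a = 0, nominal 5%**

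| z_b | Delta | Monte Carlo |
|---|---|---|
| 2 | 0.4% | 1.9% |
| 3 | 1.1% | 3.7% |
| 4 | 2.2% | 4.7% |
| 6 | 3.7% | 5.0% |
| 8 | 4.3% | 5.0% |

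The extra power is therefore not bought with an inflated error rate.

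**H3 as the text defines it** (4,000 replicates, 4,000 draws each, covariance of b and d included). At N = 900 and d_a = 0.3:
- (b, c, d) = (−0.05, −0.1, 0.2): power rises from 27.4% to 47.9%.
- (b, c, d) = (−0.1, −0.3, 0.4): power rises from 86.8% to 89.0%.

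With a = 0, over the settings run, the delta test rejects in 0 to 4.4% and the Monte Carlo interval in 0.9 to 5.5% (simulation error about 0.3 points).

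**H3 as coded, with a = 0**, so that condition has no indirect effect at all:

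| N | b | c | d | Delta | Monte Carlo |
|---|---|---|---|---|---|
| 1500 | −0.05 | −0.1 | 0.2 | 81% | 79% |
| 450 | −0.05 | −0.1 | 0.2 | 24% | 22% |
| 1500 | −0.1 | −0.3 | 0.4 | 100% | 100% |

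The coded quantity contains c × d whether or not the intervention does anything, so it rejects because protective strategies relate to drinking and drinking relates to problems.

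**The case against.** **The delta test is inferred.** The SAP never names it, and the printed code is visibly incomplete: the covariates promised in the text (week, number of drinking days, sex) are not in it. A missing interval request is thus weak evidence of intent. This stands. If another test was meant, though, the SAP still needs the sentence that names it.

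**The delta test is valid.** It does not inflate type I error for H2, and many analysts use it. This also stands: the point is recoverable power, not an error that would mislead.

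**The gain rests on path b, which the documents do not size.** Correct. With a strong b the gain is a point or two, and no choice of interval removes the ceiling set by path a.

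**Joint significance of a and b does as well for H2 and needs no script.** True: at N = 900, d_a = 0.3, |b| = 0.10 it gives 76.0%, against 74.3% for Monte Carlo. But it gives no interval, and for H3 the factor multiplying a is b + c × d, which itself contains a product.

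**A stronger reading that fails.** A reader might infer that H2 and H3 as programmed both run well below their nominal error rate. The documents do not support that for H3. The conservatism belongs to the text's formula, whereas the coded formula errs in the opposite direction, and a Monte Carlo interval built on it keeps the error. Nor do the documents support a fixed power loss for this trial.

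**Conclusion.** The point holds for H2 and for H3 as written in the text: the test that the code implies is conservative when the paths are imprecise. The avoidable loss for H2 is about 0 to 19 points of power, and about 2 to 20 points in the two H3 settings shown. A Monte Carlo interval recovers it within the nominal error rate, apart from simulation error.

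This rests on two-sided 5%, equal arms, normal estimates, path a independent of the other paths, and assumed sizes for the paths and the analysed sample. It is a worthwhile, cheap improvement and not a threat to validity. The omission of path a from the coded H3 is the more serious matter and has to be settled first.

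**What to change.** 1. Reconcile the coded H3 with the text, so that Model Constraint computes a × b + a × c × d.
2. State in the SAP that H2 and H3 are tested at two-sided alpha 0.05 with 95% Monte Carlo confidence intervals, drawn from the MLR estimates of a, b, c and d and their robust covariance matrix, and that each effect is significant when its interval excludes zero.
3. Request TECH3 output, so that the covariances (including b with d) are available, and state the number of draws and the seed.

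The cost is a corrected line of code, a sentence or two in the SAP, one output request and a short script. Data collection and participant burden do not change. If path b proves precise, the two methods will nearly agree and little is gained.

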## Participants

Participants will be recruited via the Texas A&M University online research subject pool (SONA). To be included in the study procedures and subsequent data analyses, participants must be 18 or older and complete all parts. There are no exclusion criteria for participation in the baseline study (part 1). However, participants who do not follow the instructions for the specific writing task will be unable to sign-up for the remaining follow up sessions (Parts 2-6) and will be excluded from the final data analyses. For Part 1, they will be provided with a link to the Qualtrics survey (if completing online) or will sign up via SONA for an in-person lab session. For Parts 2-5, participants will be able to sign up after successfully completing the prior session; however, if they do not successfully complete the writing prompt requirements outlined in Part 1, then they will be unable to continue on to the remaining study sessions (parts 2-6). If this is the case, then the researchers involved in this study will contact participants to let them know their remaining follow-up sessions will be canceled, but will still receive credit for what they have completed.

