L2PBS on NegEventcondition;

L2Drinks on L2PBS(c);

Problems on L2PBS(b);

Problems on L2Drinks(d);

Model Constraint:

New(H1 H2 H3);

H1 = a;

H2 = a*b

H3 = H2+(c*d);

Exploratory Analysis: We will examine differences between the counterfactual condition and PBS PNF condition to determine equivalence between the two intervention effects. This approach will use a two one-sided equivalence test (TOST), to compare the two active treatments (Lakens, 2017). This allows for a comparison of a new treatment against the observed effects of an existing treatment (rather than against the traditional null hypothesis). In doing so, we will specify an “equivalence” margin of Cohen’s d -0.20 to 0.20 (a small effect in both directions). We will then calculate 95% confidence intervals of the effect size difference between the Counterfactual and PBS-PNF. A positive value indicates a stronger effect of Counterfactual relative to PBS PNF, while a negative value indicates a weaker effect. This approach allows for the statistical determination of whether the observed effect is equivalent to the standard treatment, superior to the standard treatment, or inferior to the standard treatment.

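### The Mplus line for H3 omits path a from its second term, so the coded H3 can be significant when the counterfactual task has no effect

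*SAP*

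**What the plan says.** The SAP states Hypothesis 3 in words and as a formula. In words: "Relative to control, the counterfactual condition will exert a significant total indirect effect on alcohol problems through PBS use and alcohol use". The formula beside it adds to H2 the product of three paths, a × c × d. H2 is defined just above it as "H2 = path a x path b". The text H3 is therefore a × b + a × c × d.

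The Mplus code in the same SAP attaches the labels as follows:
- a: "L2PBS on CFcondition(a", the effect of the counterfactual condition on between-person PBS use;
- b: the regression of problems on between-person PBS use;
- c: "L2Drinks on L2PBS(c", the regression of between-person drinking on PBS use;
- d: "Problems on L2Drinks(d", the regression of problems on between-person drinking.

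Under Model Constraint, H1 is set to a and H2 to `a*b`, both as in the text. H3 is set to `H2 + (c*d)`. The factor a that the text puts in the second term is absent.

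**The concern.** H3 is a claim about a randomised condition compared with control. In the coded version, the second term is the association of PBS use with drinking multiplied by the association of drinking with problems, estimated across all arms. No randomised contrast enters it.

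That association is likely to be non-zero for reasons unrelated to the intervention: the SAP's own model has PBS use predicting drinking and alcohol consequences. If people who use more PBS drink less (c < 0) and people who drink more have more problems (d > 0), c × d is negative, which on this outcome reads as benefit. The trial could then report a significant total indirect effect of the counterfactual task that comes from the observational part of the model. The faulty line looks like a legitimate constraint and would return a plausible estimate and p-value, so nothing in the output would flag it.

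**Working it through.** **Inputs.** The two H3 formulas and the four labels come from the SAP. The documents give no path values, no alpha for H1–H3 and no analysed N, and there is no stated H3 figure to reproduce. Everything numerical below rests on assumed values. Planned enrolment is about 1500 (Protocol 9.1). The analysed N should be smaller, because the Protocol's Participants section says "participants must be 18 or older and complete all parts" (although 9.6 and 15.2 allow later waves fewer sessions) and the SAP says "Only weeks during which participants consume alcohol will be included in the analysis". N = 1500 is therefore an upper bound.

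**Algebra.**
- Text: H3 = ab + acd.
- Code: H3 = ab + cd.
- Code minus text = cd − acd = cd(1 − a).
- At a = 0: text = 0, code = cd.

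The two agree only if a = 1 or cd = 0.

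**Point values under assumed paths** (negative means fewer problems).

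| a | b | c | d | Text: ab + acd | Code: ab + cd |
|---|---|---|---|---|---|
| 0.2 | −0.15 | −0.2 | 0.4 | −0.030 − 0.016 = −0.046 | −0.030 − 0.080 = −0.110 |
| −0.2 | −0.15 | −0.3 | 0.5 | +0.03 + 0.03 = +0.06 | +0.03 − 0.15 = −0.12 |
| 2 | −0.05 | −0.1 | 0.4 | −0.10 − 0.08 = −0.18 | −0.10 − 0.04 = −0.14 |

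In row 1 the benefit is overstated by a factor of 0.110/0.046 = 2.4. In row 2 the condition lowers PBS use and raises problems, yet the code shows benefit. In row 3 a exceeds 1 and the code understates the benefit.

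**Rejection rates when a = 0.** Simulated with a single-level analogue of the between-person model: four equal arms, b = −0.15, delta-method z test, two-sided alpha 0.05, 2000 trials per setting. Where repeat runs differed, a range is shown or the rate is marked as approximate.

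| c, d | Coded H3, N = 400 | N = 800 | N = 1500 |
|---|---|---|---|
| −0.2, 0.4 | 72–74% | 93–95% | 100% |
| −0.1, 0.3 | 19% | 37% | 59–61% |
| −0.05, 0.2 | about 4% | about 8% | about 13% |
| 0, 0.4 | about 4% | 4–5% | about 4% |

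The text formula rejects in about 2–5% in the first setting and stays close to or below 5% in the others. In the harmful case (row 2 of the point values), the coded H3 is significant for benefit in 84–86% at N = 400 and 98–99% at N = 800.

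**Hand check of the first entry.** Take unit residual SDs and N = 400, so 100 per arm.
- Var(a) = 1/100 + 1/100 = 0.02; Var(c) and Var(d) are each about 1/400 = 0.0025.
- At a = 0 the delta-method variance of the coded H3 is b²Var(a) + d²Var(c) + c²Var(d) = 0.00045 + 0.00040 + 0.00010 = 0.00095, so the SE is 0.031.
- z = −0.08/0.0308 = −2.60, and the chance of exceeding 1.96 in size is about Φ(0.64) = 74%, in line with the simulation.

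**The case against.** Several points can be made on the other side, and some stand.

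- **The estimand is correctly specified.** A reader might infer that the code is the only operational definition of H3. It is not: the right formula is printed inside Hypothesis 3. The defect is a code line that departs from a correct definition in the same document.
- **Inflation is not universal.** A reader might infer that any non-zero c and d break the type I error rate. At c = −0.05, d = 0.2 and N = 400 the coded test rejects in about 4%. The supportable statement is that the rate can be exceeded, by an amount that depends on c, d and N.
- **The code need not overstate a real benefit.** With cd < 0 it does so only if a < 1. The printed code labels raw coefficients and requests no standardisation, and the SAP does not say how PBS is scored, so a > 1 cannot be excluded.
- **The percentages are illustrative.** They come from a single-level analogue, not the planned two-level MLR model. The algebra does not depend on that choice.
- **The code looks unfinished.** The covariates named in the SAP do not appear in it, and the H2 line shows no closing semicolon (possibly lost in reading the PDF). The code may well be edited before use, but neither correction would restore path a.

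A reader might also infer that a reported H3 result is already wrong. The documents do not say whether the printed code has been run.

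**Conclusion.** The point holds. The Model Constraint line for H3 contradicts the SAP's own definition by leaving path a out of the second term, and no other part of the documents puts it back. When the counterfactual task has no effect, the coded quantity is c × d instead of 0, so H3 can be declared significant with no intervention effect, or in favour of a condition that lowers PBS use.

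The existence and form of the error follow from algebra alone. Its practical size does not: across the assumed paths, false rejection of the coded H3 runs from no inflation to near certainty. Larger samples make it worse whenever c × d is not zero. The error is confined to H3, one of the SAP's three numbered hypotheses; H1 and H2 match their text.

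**What to change.** Change the Model Constraint line to `H3 = H2 + (a*c*d);`, which is what the Hypothesis 3 text already specifies. With that line H3 is exactly 0 when a = 0, and simulated rejection under a = 0 stayed at or below 4.8% for N from 200 to 1500 in one set of assumed paths. If the printed code has been used, re-run H3 and replace the result.

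The cost is one line of code and at most one re-run. The hypothesis, design and data collection do not change.

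### Hypothesis 3 tests the sum of two indirect routes, so a significant H3 cannot by itself show mediation through alcohol use, and the SAP plans no test of that route alone

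*SAP*

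**What the plan says.** Hypothesis 2 in the SAP is that, relative to control, "the counterfactual condition will exert a significant specific indirect effect on alcohol problems through PBS", with H2 = a × b. Hypothesis 3 is that "the counterfactual condition will exert a significant total indirect effect on alcohol problems through PBS use and alcohol use", with H3 = H2 + a × c × d. The text thus separates a specific effect (H2) from a total effect (H3) and prints the sum openly.

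The Statistical Design paragraph has condition predicting PBS, and PBS then predicting both alcohol use and its consequences. The between-person code has the same structure: a direct path from PBS to problems and a path that runs through drinks. The Model Constraint block creates three derived parameters only: H1, H2 and H3. None of them is a × c × d, and the SAP gives no rule for reading c and d when interpreting H3.

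The H3 line in the code also departs from the text: its second term is c × d, without path a.

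**The concern.** Only the a × c × d term of H3 passes through alcohol use. H3 is judged on the sum, so a significant result does not show which term produced it. Suppose the counterfactual task makes drinking safer without changing how much is drunk. Then a × b is real and a × c × d is zero, yet the trial could report Hypothesis 3 as met in a sentence that names alcohol use as a route. The reverse can also happen: if the routes oppose each other, H3 can fail while mediation through alcohol use is real. What is at stake is the mechanism the trial may claim. The false-positive rate of H3 as written in the text is not at issue.

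**Working it through.** **Inputs from the SAP code** (closing brackets cut from the quotes)
- a: "L2PBS on CFcondition(a", condition to PBS
- b: "Problems on L2PBS(b", PBS to problems
- c: "L2Drinks on L2PBS(c", PBS to drinks
- d: "Problems on L2Drinks(d", drinks to problems

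**Algebra, no assumptions needed**
- H2 = a × b.
- H3 (text) = a × b + a × c × d = a × (b + c × d).
- If c = 0 or d = 0, then H3 = a × b = H2. The coded version, a × b + c × d, also reduces to H2.
- If b = −c × d, then H3 (text) = 0 for any a, even when a × c × d is not zero.

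**Size, which needs assumptions.** The documents give no path sizes, alpha or sidedness for H1–H3. Protocol section 9.1 plans 1500 participants, with no effect size, power or attrition rate, so there is no planned figure to reproduce. The simulation covered the between-person paths only: four equal arms, unit residual SDs, ordinary least squares, delta-method z tests at two-sided 0.05, and 2000 runs per setting. Arm sizes were 100, 200 and 375. The last is 1500 / 4, an upper limit that assumes equal allocation and no losses. Simulation error near 76% is about sqrt(0.76 × 0.24 / 2000) = 1 percentage point.

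Percentage of runs significant at 100 / 200 / 375 per arm, with a = 0.4 and H3 as the text defines it:

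| Setting | a × b | a × c × d | H3 | H2 sig. | H3 sig. | a × c × d sig. |
|---|---|---|---|---|---|---|
| No alcohol route: b = −0.3, c = 0, d = 0.4 | −0.12 | 0 | −0.12 | 76 / 98 / 100 | 75 / 98 / 100 | 0.8 / 2.6 / 3.2 |
| No alcohol route: b = −0.3, c = −0.3, d = 0 | −0.12 | 0 | −0.12 | 76 / 98 / 100 | 77 / 98 / 100 | 0.4 / 1.6 / 3.3 |
| Both routes: b = −0.3, c = −0.3, d = 0.4 | −0.12 | −0.048 | −0.168 | 75 / 98 / 100 | 77 / 98 / 100 | 74 / 97 / 100 |
| Alcohol route only: b = 0, c = −0.3, d = 0.4 | 0 | −0.048 | −0.048 | 1.0 / 2.2 / 3.8 | 29 / 78 / 98.5 | 77 / 98 / 100 |
| Opposed routes: b = 0.12, c = −0.3, d = 0.4 | 0.048 | −0.048 | 0 | 28 / 79 / 99 | 0.8 / 1.8 / 3.2 | 74 / 97 / 100 |

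The first three rows carry the point. H3 is significant about equally often with and without an alcohol route, whereas the direct test of a × c × d separates the cases. In the first two rows, when H2 was significant H3 was too in at least 98.6% of runs.

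With a smaller effect (a = 0.3, b = −0.3, c = −0.3, d = 0; 100 / 200 / 300 per arm) the pattern is the same: H3 significant in 51 / 85 / 96%, a × c × d in 0.5 / 1.3 / 1.4%.

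**Error rate and the code line.** With a = 0, b = −0.3, c = −0.3, d = 0.4, text-H3 is significant in 4.3 / 5.0 / 5.1% of runs, so its own null is controlled. In the same setting the coded H3 has true value 0 + (−0.3 × 0.4) = −0.12 and is significant in 67 / 92 / 99.8%, although the condition does nothing.

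**The case against.** The strongest reply is that H3 does what it says. A total indirect effect is the sum over the mediated routes, the SAP uses that term and prints the sum, and naming PBS use and alcohol use can be read as listing the mediators covered. This stands: the text does not contradict itself, and nowhere does it say that a significant H3 proves mediation by alcohol use. What remains is that the hypothesis names alcohol use and no planned test bears on that part alone.

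A second reply is that c and d are labelled and will appear in the output. They will, but without a stated rule their use would be decided after the results are seen.

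A third is that the code line is the more serious H3 defect. It is, and it is separate: coding H3 exactly as the text defines it leaves this point unchanged.

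A reader might also infer more than the documents support:
- **That H3 is met automatically with H2, or adds almost no evidence of its own.** Both fail once c × d is not zero. With opposed routes H2 is significant in 28–99% of runs and H3 in 1–3%. With the alcohol route only, H2 is significant in 1–4% and H3 in 29–98.5%.
- **That H3 has no error control.** Text-H3 rejects in 4–5% of runs when a = 0.
- **That the serial chain is the SAP's only causal chain.** The Statistical Design paragraph and the code both include a direct route from PBS to problems, so the sum is a legitimate target. Figure 1 is not available to settle the intent further.

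**Conclusion.** The point holds as one of attribution. H3 in the text is a valid total indirect effect, but a significant H3 cannot by itself support mediation through alcohol use, a null H3 cannot rule it out, and no prespecified test covers that part of the claim. The identities (H3 = H2 when c × d = 0; H3 = 0 when b = −c × d) need no assumptions. The percentages rest on assumed path sizes, alpha and arm sizes, and on a single-level approximation to a two-level MLR model restricted to drinking weeks. They illustrate the size and do not forecast this trial. The change is worth making because it is cheap and alters what the trial may conclude.

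**What to change.** When the H3 code line is reconciled with the Hypothesis 3 text, which has path a in the second term:
1. Add `H3serial` to the list of new parameters and define it in Model Constraint as a × c × d.
2. Keep H3 = a × b + a × c × d and report it as the total indirect effect.
3. Add a sentence to Hypothesis 3 saying that mediation through alcohol use will be concluded only if `H3serial` is significant.

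The cost is one code line, one name in the parameter list and one sentence, with no new data. The downsides are one more test and that H3 alone no longer supports the alcohol-use statement. Under the assumptions above, the added test detects a real alcohol route in 74 / 97 / 100% of runs at 100 / 200 / 375 per arm with a = 0.4, and in 49 / 83 / 95% at 100 / 200 / 300 per arm with a = 0.3 (b = −0.3, c = −0.3, d = 0.4 in both).

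### The exploratory equivalence test can call the counterfactual task equivalent to standard treatment without any evidence that PNF works in this trial

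*SAP*

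**What the plan says.** The SAP's Exploratory Analysis sets up the comparison of the two active arms: "This approach will use a two one-sided equivalence test (TOST), to compare the two active treatments". It gives the purpose of the method as follows: "This allows for a comparison of a new treatment against the observed effects of an existing treatment". The margin is Cohen's d from −0.20 to +0.20. The interval is specified as follows: "We will then calculate 95% confidence intervals of the effect size difference between the Counterfactual and PBS-PNF". The SAP says the result will determine "whether the observed effect is equivalent to the standard treatment, superior to the standard treatment, or inferior to the standard treatment". It states no condition on how either arm compares with control.

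The Mplus code contains the line "L2PBS on PBSPNFcondition", which estimates PNF against whichever arm has no indicator variable. Indicators are listed for CF, PNF and the negative-event-only arm, so the omitted arm is negative event plus fact listing. The PNF path has no label, does not enter Model Constraint and belongs to no hypothesis.

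Hypothesis 1 has two parts joined by 'and'. The first is "Relative to control, the counterfactual condition will result in significantly more use of PBS during drinking days". The second is that the CF arm "will be *at least* non-inferior to PBS personalized normative feedback". The only test named for the pair is path a, which is CF against the omitted arm. The SAP does not say which of the two negative-event arms is control.

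**The concern.** A finding of equivalence to a reference treatment supports efficacy only if the reference is effective in the same trial (assay sensitivity). Here the TOST looks only at CF minus PNF. If neither task changes PBS use, the true difference is zero, which is where the test is most likely to pass. A report could then describe an inert task as equivalent to standard treatment, and readers would take that as evidence of benefit.

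It is not safe to presume that PNF works here. Protocol 8.1 describes Condition 4 as a single Part 1 task in which participants rate other students' PBS use, and that description mentions no feedback being returned. All arms answer PBS norm questions after the manipulation and at each follow-up, and all complete the PBS-20 and PBS intentions weekly, so contrast with control may be small. The exact task is in attachments not available here and may include feedback. PNF's effect is therefore something to check, and the trial has the control arms to check it.

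**Working it through.** **No plan figure to reproduce.** Protocol 9.1 gives 1500 participants and refers to adequate power, but states no effect size, alpha, power or dropout rate.

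**Inputs from the documents.** Enrolment 1500 (Protocol 9.1); four arms (Protocol 8.1, Procedure); margin ±0.20 and a 95% interval (SAP, Exploratory Analysis).

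**Assumptions.** Equal allocation (the ratio is not stated), so 1500/4 = 375 per arm at full retention; one independent summary value per person with SD 1; true CF-PNF difference of zero. The SAP gives no one-sided alpha for the TOST, so the 95% interval (z = 1.96) and the 90% interval (z = 1.645) are both shown.

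**Formula.** SE = √(2/n). Equivalence is declared when the interval lies wholly inside ±0.20. At a true difference of zero:

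P(equivalence) = 2Φ(0.20/SE − z) − 1, floored at 0.

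At n = 375, SE = √(2/375) = 0.0730 and 0.20/SE = 2.739.
- 95% interval: 2Φ(2.739 − 1.960) − 1 = 2(0.782) − 1 = 0.564.
- 90% interval: 2Φ(2.739 − 1.645) − 1 = 2(0.863) − 1 = 0.726.

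The interval cannot fit inside the margin when z·SE ≥ 0.20, that is when n ≤ 2(z/0.20)². This is 192.1 for the 95% interval and 135.3 for the 90% interval.

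**Results.** The last two columns also require PNF to beat control (two-sided 0.05). They come from a simulation of 1,000,000 replicates with three equal-mean arms of equal size.

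| Retention | n per arm | 95% rule | 90% rule | 95% rule and PNF > control | 90% rule and PNF > control |
|---|---|---|---|---|---|
| 100% | 375 | 56% | 73% | 0.8% | 1.2% |
| 80% | 300 | 38% | 58% | 0.5% | 0.8% |
| 60% | 225 | 13% | 37% | 0.2% | 0.5% |
| 50% | about 187 | 0% | 23% | 0% | 0.3% |
| 40% | 150 | 0% | 7% | 0% | 0.1% |

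An even chance of declaring equivalence needs 348 per arm on the 95% rule or 269 on the 90% rule.

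**Hypothesis 1.** In the same simulation, with all arms inert, CF beats control and also clears the −0.20 bound in 2.1% to 2.5% of replicates across these sample sizes. The first clause limits this: the chance of CF beating control in error is 2.5% on one side.

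**Cost of the condition.** If PNF truly has d = 0.20 against control, power is Φ(0.20/SE − 1.96). At 375 per arm this is Φ(0.779) = 0.78, so the condition is missed about 22% of the time. At 250 per arm, SE = 0.0894 and power is Φ(0.276) = 0.61, so it is missed about 39% of the time.

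**The case against.** **The percentages are not error rates.** At a true difference of zero the arms are equivalent, so 56% and 73% are the TOST's power at that point and would be the same if both tasks worked equally well. This stands as a matter of definition. It also states the problem: the test gives the same answer in both situations, so it cannot support a claim of efficacy unaided.

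**A reader might infer that two inert tasks would often be declared equivalent.** The documents do not support that word. Protocol 9.1 expects non-qualifiers and attrition, the Participants section of Protocol 8.1 requires completion of all parts and excludes those who do not follow the writing instructions, and the SAP keeps only drinking weeks. Analysed numbers could be well below 375 per arm, and on the 95% rule the event is impossible below about 193. A small sample makes the TOST unable to conclude equivalence; it does not make an equivalence verdict more meaningful.

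**A reader might also infer that Hypothesis 1 is equally exposed.** The −0.20 bound taken alone would be cleared 78% of the time at 375 per arm with inert tasks, but Hypothesis 1 does not take it alone. It also requires CF to beat control, which brings the joint chance down to about 2.5%. What remains is narrower: Hypothesis 1 never requires PNF to beat control, and path a does not involve PNF.

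**The analysis is labelled exploratory, and the PNF estimate will appear in the output anyway.** Both points stand. They lower the severity and mean that labelling the path adds little. What is missing is a stated rule for reading the result.

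**A strict condition could discard a valid comparison.** This also stands. A real PNF effect of d = 0.20 could miss significance, so it would be too strong to call the CF-PNF interval uninterpretable in that event.

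**Conclusion.** The concern holds for the exploratory TOST. As written, equivalence to standard treatment can be concluded from the CF-PNF contrast alone, and the estimate that would show whether PNF works is used nowhere. For two inert tasks the chance of that conclusion runs from 56% at 375 per arm to zero below about 193 on the 95% interval, and from 73% to zero below about 136 on the 90% interval. These figures assume equal allocation, SD 1 and independent per-person summaries. Clustering and adjustment for sex would change the SE, so they are illustrative. Where the true rate falls depends on an analysed sample size that the documents do not give. Hypothesis 1 shares only the narrower gap. Because the analysis is exploratory and the remedy is wording, severity is modest.

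**What to change.** 1. State which negative-event arm is control. The code as written makes fact listing the reference; if the other arm is meant, PNF versus control needs the corresponding contrast.
2. Report PNF versus that control on PBS use, with its interval, beside the TOST. Labelling the path is convenient but optional.
3. State before results are seen that equivalence to standard treatment will be claimed as evidence of benefit only if PNF is better than control on PBS use. Apply the same reading to the non-inferiority part of Hypothesis 1.
4. If PNF is not shown to be better, still report the CF-PNF difference and its interval, and say that assay sensitivity was not shown, so similarity cannot be read as efficacy.

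The cost is a few sentences in the SAP and no new data. The equivalence claim becomes harder to make, and a real but small PNF effect may miss the condition: about 22% of the time at 375 per arm and 39% at 250 if d = 0.20. Step 4 limits that loss by keeping the comparison in the report.
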